## 12.5.2. Tertiary Analyses (given sufficient number of events, >15 events in total for both treatment arms, are available for analyses to be meaningful)

- Composite of ischemic stroke, MI, all-cause death, or major hemorrhage
- Composite ischemic stroke, TIA, MI, or ischemic vascular death
- TIA (as outcome)

- Coronary Revascularization
- Vascular death
- SAEs together and by major class (MedDRA Body System)
- New handicap/disability defined as 90 day mRS (>=2)
- 90 day mRS (ordinal)
- Asymptomatic intracranial hemorrhage (ICH, SAH, SDH or IVH)

These analyses are used to confirm or support the findings based on the primary outcome analysis. If most of the secondary outcomes show a change in the opposite direction from the primary or no change, we might have less confidence in the primary outcome.

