### 12.4. Interim Monitoring Schematic

### 12.5. Secondary and Tertiary Clinical Efficacy Outcomes Analyses

### 12.5.1. Secondary Analyses

Several secondary analyses will be performed to evaluate of the impact of therapy. Prior to these analyses, univariate analyses of covariates, identified from previous studies as having confounding effect on the outcome measurements, are conducted to determine their inclusion in the multivariable models. In addition, stepwise regression methods may be applied to assess the best set of covariates to include in a particular model. Some of the suspected significant confounders are: age, time from symptom onset to randomization, African Americans, those previously taking aspirin, those with index TIA vs. minor ischemic stroke.

The usual verification of variable and model assumptions and goodness of fit assessments accompany each analysis. Time to event outcomes will be assessed via log rank test (unadjusted) and via cox proportional hazard model adjusting for covariates. A Wilcoxon log-rank test will be used for ordinal outcomes (mRS). A logistic regression will be used for binary outcomes (90 day mRS). The significance of each test is set at a two-sided alpha of 0.05.

ITT analyses and As-treated analyses will be performed for the following secondary outcomes for efficacy/net-benefit:

- Composite event of ischemic stroke, MI, ischemic vascular death, or major hemorrhage
- Ischemic stroke
- Ischemic vascular death
- MI
- Composite event of ischemic stroke and hemorrhagic stroke

ITT analyses and As-treated analyses for efficacy/net-benefit will be performed for the following secondary outcomes for safety/tolerability:

- Primary efficacy outcome from day 0 to 7 and day 8 to 90, and from day 0 to 30 and day 31 to 90 (HR and 95% CI will be calcuated via cox model for each time point stratified)
- Primary safety outcome from day 0 to 7 and day 8 to 90, and from day 0 to 30 and day 31 to 90 (HR and 95% CI will be calcuated via cox model for each time point stratified)
- All-cause Death
- Hemorrhagic stroke
- Symptomatic intracerebral hemorrhage
- Other symptomatic intracranial hemorrhage (SAH, SDH or IVH)
- Major Hemorrhage other than Intracranial Hemorrhage
- All minor hemorrhage (including asymptomatic intracranial hemorrhage)

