### 13.2 Summary of Adverse Events

All SAEs are summarized by "preferred term" and associated system-organ class according to the MedDRA adverse reaction dictionary and by treatment group in terms of frequency of the event, number of subjects having the event, timing relative to randomization, severity, and relatedness to the study drug.

For the following specific events, the proportions and their 95% confidence intervals by treatment group are provided:

- Death from any cause within 90 (± 14) days of randomization (expected rate 3%)
- Intracranial hemorrhage within 90 days (expected rate 0.5%)
- Major hemorrhage within 90 days (expected rate 2%)
- Minor hemorrhage within 90 days (expected rate 2%)

Expected rates of these events are based on historical data from the clopidogrel treated patients from pilot cohort studies ([name], et al., 2000; 2007), and these expected rates will be presented alongside the actual rates.

Other serious adverse events will be reported by treatment group. At the end of the study, the cumulative incidences of these events are compared between the two treatment groups using Fisher's exact test at the two-sided alpha level of 0.01.

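### SAP 12.5.2 allows the separate comparison of asymptomatic intracranial hemorrhage only above 15 pooled events, so a lopsided small split of this harm would get no between-arm test of its own

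*SAP*

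**What the plan says.** The heading of SAP 12.5.2 makes the tertiary analyses conditional: "given sufficient number of events, >15 events in total for both treatment arms, are available for analyses to be meaningful". No derivation of the cut-off is given, and no fallback is stated for an outcome that misses it. The list under that heading includes "Asymptomatic intracranial hemorrhage (ICH, SAH, SDH or IVH").

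The same bleeds also appear, or may appear, in places that carry no event minimum:

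- SAP 12.5.1 has the secondary safety outcome "All minor hemorrhage (including asymptomatic intracranial hemorrhage"), analysed ITT and as-treated. On testing it says: "The significance of each test is set at a two-sided alpha of 0.05". Table A.3 codes asymptomatic intracerebral and other asymptomatic intracranial hemorrhage into this outcome.
- SAP 13.2 lists intracranial hemorrhage (expected rate 0.5%, not qualified by symptoms) and minor hemorrhage (expected rate 2%) among events for which "the proportions and their 95% confidence intervals by treatment group are provided". It then says that "the cumulative incidences of these events are compared between the two treatment groups using Fisher's exact test", at two-sided 0.01. The sentence before that one concerns other SAEs, so it is unclear whether the test covers the listed events or only the other SAEs.

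**The concern.** A minimum number of events is sensible before fitting a Cox model. It is a poor condition for deciding whether to compare a rare harm at all. If the drug causes nearly all the events, the placebo count is close to zero and the total stays small precisely because the split is extreme. An exact test is valid at any count, so 15 or fewer events can still be informative.

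At stake is the one between-arm comparison that isolates silent intracranial bleeding. The protocol defines this outcome (4.6.1) and sends it to two neurologist adjudicators (8.5.5). Under the rule as written, those adjudicated data could end with no comparison of their own.

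**Working it through.** **Inputs.** Maximum sample size 5,840 (SAP 5.3), randomized 1:1 (SAP 4), so 5,840 / 2 = 2,920 per arm. The condition is more than 15 events in total (SAP 12.5.2). Expected rates are 0.5% for intracranial and 2% for minor hemorrhage (SAP 13.2). The SAP gives no rate for asymptomatic intracranial hemorrhage alone, so rates for it below are assumptions. The cut-off of 15 has no stated inputs, so there is no plan figure to reproduce; only its consequences can be checked.

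**1. Are splits below the cut-off informative?** Two-sided Fisher's exact test, 2,920 per arm. With rare events and equal arms this is close to 2 × P(Binomial(total, 1/2) ≤ smaller count). For 14 v 1 that is 2 × (1 + 15) / 2^15 = 0.00098; the exact value is 0.00096.

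| Split | Fisher p |
|---|---|
| 15 v 0 | 0.00006 |
| 14 v 1 | 0.001 |
| 13 v 2 | 0.007 |
| 12 v 3 | 0.035 |
| 11 v 4 | 0.12 |
| 8 v 0 | 0.008 |
| 6 v 0 | 0.031 |

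The smallest one-sided split below 0.05 is 6 v 0; below 0.01 it is 8 v 0.

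**2. Could the condition fail?** It needs at least 16 events: 16 / 5,840 = 0.27% pooled. With a Poisson total of mean 5,840 × rate:

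| Assumed pooled rate | Expected total | P(more than 15) |
|---|---|---|
| 0.1% | 5.8 | <0.1% |
| 0.2% | 11.7 | 13% |
| 0.25% | 14.6 | 39% |
| 0.3% | 17.5 | 67% |
| 0.5% | 29.2 | 99.7% |

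The last row is the SAP's rate for intracranial hemorrhage without qualification. If silent bleeds were half of that or less, the condition would more likely fail than be met.

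**3. How often would a significant excess be blocked?** Independent Poisson counts: placebo mean = 2,920 × background, clopidogrel mean = that × risk ratio. A trial counts as blocked if the total is 15 or fewer and Fisher p < 0.05 towards harm.

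| Background | Risk ratio | Means (placebo, clopidogrel) | Blocked |
|---|---|---|---|
| 0.05% | 2 | 1.46, 2.92 | 2% |
| 0.1% | 2 | 2.92, 5.84 | 8% |
| 0.2% | 2 | 5.84, 11.68 | 5% |
| 0.05% | 6 | 1.46, 8.76 | 49% |
| 0.1% | 6 | 2.92, 17.52 | 10% |

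In the last row the expected total is 20.44, so the condition is usually met. At the 0.01 level of SAP 13.2, the 49% falls to 24%.

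**4. Do the other outcomes show the excess?** It depends on what it is pooled with.

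- All minor hemorrhage, assuming 2,920 × 2% ≈ 58 other minor bleeds in each arm: 15 v 0 becomes 73 v 58, p = 0.22; 13 v 2 becomes 71 v 60, p = 0.38.
- The same with clopidogrel also raising other minor bleeding: at ratio 1.3 (58 × 1.3 ≈ 75) 13 v 2 becomes 88 v 60, p = 0.024; at ratio 1.7 (58 × 1.7 ≈ 99) it becomes 112 v 60, p < 0.001. The composite is then positive, but it does not show whether the brain is involved.
- Intracranial hemorrhage in SAP 13.2, if it includes silent bleeds: 15 v 0 added to 3, 5 or 10 others per arm gives p = 0.001, 0.004 or 0.016.

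**The case against.** The best defence is that little is lost. The bleeds are tested within all minor hemorrhage, and on the natural reading of an unqualified label they are reported by arm with intervals in SAP 13.2. Closed DSMB reports are by treatment group (SAP 2). The rule does not forbid printing counts, and a minimum for exploratory models is ordinary practice. Secondary results are called supportive and exploratory (SAP 9), and 12.5.2 gives its own analyses a supportive role. Follow-up head imaging is standard care (protocol 1.2), so silent bleeds would be found incidentally. All of this stands, and it is why the point is small.

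It does not remove the point. None of these routes isolates the outcome, and 13.2 does not say whether silent bleeds are included.

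Three stronger readings are tempting, and the documents do not support them:

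- *The harm goes uncompared.* It does not; it enters an outcome with no event minimum.
- *SAEs by MedDRA class are suppressed too, in conflict with 13.2.* Section 13.2 tabulates all SAEs by class and arm without a minimum. The condition only limits an additional tertiary analysis, and both sections can be followed as written.
- *The excess would usually be diluted away, or blocked about half the time.* The dilution results of p = 0.22 and 0.38 assume that clopidogrel does not affect other bleeding, whereas protocol 2.4 cites total bleeding of 10.1% on the combination against 4.8% on aspirin. They also apply to both arms expected rates that 13.2 takes from clopidogrel-treated patients. The 49% rests on one pair of assumed values. The cited bleeding ratios are nearer 2 (10.1 / 4.8 = 2.1; major bleeding 1.7% / 1% = 1.7), where the figure is 2-8%.

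**Conclusion.** The point holds in a limited form and is a cheap improvement. The condition in 12.5.2 can remove the only separate comparison of asymptomatic intracranial hemorrhage even when the split is clear (14 v 1, p = 0.001). The pooled outcomes that still contain the events may or may not reveal it.

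The chance that this matters cannot be fixed from the SAP. Over the assumed ranges it is about 2-8% at risk ratio 2 and 10-49% at risk ratio 6, at two-sided 0.05 and with 2,920 per arm.

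A reader might infer that the trial's weighing of benefit against bleeding is compromised. It is not. Major hemorrhage, its composite with the primary outcome, symptomatic intracerebral and other symptomatic intracranial hemorrhage, hemorrhagic stroke and all-cause death are all free of the condition, and silent bleeds are not part of major hemorrhage (SAP 3.2, Table A.3).

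**What to change.** In SAP 12.5.2, exempt asymptomatic intracranial hemorrhage from the event condition. Always report counts and exact 95% confidence intervals by arm. When the total is 15 or fewer, compare the arms with Fisher's exact test, labelled exploratory. Keep the condition for log-rank, Cox and covariate-adjusted analyses.

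It would help to state in 13.2 whether intracranial hemorrhage includes asymptomatic bleeds and which events the Fisher test covers.

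The cost is a sentence or two in the SAP and a few more exploratory p-values. No data collection changes.

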### 13 SAFETY ANALYSES

### 13.1 13.1. Safety Monitoring

The detailed guidelines for monitoring for safety by the Medical Monitor and the DSMB are provided in the NINDS Guidelines for Data and Safety Monitoring in Clinical Trials (http://www.ninds.nih.gov/research/clinical\_research/policies/data\_safety\_monitoring.htm).

To expedite review, safety data will be analyzed by the DSMB as reported by the site investigator, prior to adjudication. The unblinded statistician at the NETT SDMC will produce the reports on a regular basis and at the request of the DSMB.

The DSMB may request an additional interim analysis of efficacy if safety concerns must be balanced against efficacy and may recommend stopping the study prior to the planned interim analysis if, in their judgment, the risk to patients outweighs the benefit of treatment. The final decision to terminate the study will be made by the NINDS, based on the DSMB recommendation.

### 13.2 Summary of Adverse Events

All SAEs are summarized by "preferred term" and associated system-organ class according to the MedDRA adverse reaction dictionary and by treatment group in terms of frequency of the event, number of subjects having the event, timing relative to randomization, severity, and relatedness to the study drug.

For the following specific events, the proportions and their 95% confidence intervals by treatment group are provided:

- Death from any cause within 90 (± 14) days of randomization (expected rate 3%)
- Intracranial hemorrhage within 90 days (expected rate 0.5%)
- Major hemorrhage within 90 days (expected rate 2%)
- Minor hemorrhage within 90 days (expected rate 2%)

Expected rates of these events are based on historical data from the clopidogrel treated patients from pilot cohort studies ([name], et al., 2000; 2007), and these expected rates will be presented alongside the actual rates.

Other serious adverse events will be reported by treatment group. At the end of the study, the cumulative incidences of these events are compared between the two treatment groups using Fisher's exact test at the two-sided alpha level of 0.01.

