### 3.2. Safety

The safety of clopidogrel when compared to placebo is evaluated by comparing rates of allcause death, intracranial hemorrhage, major hemorrhage, minor hemorrhage, and other treatment related complications and SAEs (see section 13.2).

The primary safety outcome is major hemorrhage. Major hemorrhage is one that results in symptomatic intracranial hemorrhage, intraocular bleeding causing loss of vision, need for transfusion of two or more units of red cells or equivalent amount of whole blood, need for hospitalization or prolongation of an existing hospitalization, or death. This may include bleeding events related to surgical procedures.

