### 6.2. Intent-to-Treat Sample

As the primary analysis, all efficacy and safety outcome measures are analyzed under the intent-to-treat (ITT) principle. Under this principle, the evaluable sample includes all randomized subjects, except for re-enrollers. Re-enrollers are patients who are determined to have been enrolled into the POINT trial more than once. For re-enrollers, only the data associated with the first enrollment will be counted in the primary analysis.

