### 12.1.3. Primary Efficacy Analysis (ITT)

The primary efficacy null hypothesis of the equality of survival curves is tested with the log-rank test. The overall Type I error for the primary analysis will consider two-sided alpha=0.05 significant.

The primary analysis will be intention to treat, with inclusion and treatment group defined at the randomization assignment. Missing values will remain missing and patients will be censored at their last follow-up assessment; based on projected loss rates, it is expected that only 5 subjects will be lost at 7 days and 70 subjects lost at 90 days, so the problem is relatively minor. Kaplan-Meier estimates of the cumulative risk of an event during maximum 90-day follow-up will be reported, with HRs and 95% CI calculated using Cox proportional hazards methods (to provide an estimate of treatment effect) and the log-rank test to evaluate the treatment effect. This approach is being taken to maximize the time dependent information in the trial while still acknowledging the ease of interpretation of risks. For the Cox proportional hazards method, the Efron method will be used when there are ties since this method closely approximates the exact method, but requires less computing resources.

The primary outcome is composite of ischemic stroke, MI, or ischemic vascular death occurring up to 90 days. However, the 90 day visit may occur within +-14 days of the target visit. For patients with an event, the time to event will be the days from randomization to the first adjudicated primary outcome event (if it occurred before 90 days). Events occurring after 90 days (e.g. day 91) will not be counted in the primary analysis. Patients for whom there was no event and whose follow-up visit occurred after day 90 will be censored at exactly 90 days. For patients without a 90 day visit, the censoring date will be determined by the last collected QVSFS (censoring time will be the actual days from randomization). The Kaplan Meier curves will use the actual days up to day 90. For this figure, the "# at risk" will be reported at baseline, 7 days, and 90 days.

Likewise, the ITT analysis will be repeated for the primary and secondary efficacy and safety outcomes.

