# 12.1.7. Additional Efficacy Analyses of the Primary Outcome: On-Treatment Analyses (Secondary Analysis)

To account for study treatment discontinuations prior to 90 days, the primary efficacy outcome variable will be analyzed while on-treatment only, i.e., those who are known to have permanently discontinued the study drug will be censored one day after the date known to have permanently discontinued the study drug. Furthermore, this survival

POINT Trial Statistical Analysis Plan (Version 8: Sept 2017)

analysis of the composite events outcome will analyze all randomized subjects according to the treatment that they actually received (i.e., if they were assigned to receive study drug bottle containing drug A, but due to administrative/enrollment error, received a study drug bottle containing drug B, they would be analyzed with the group they actually received). For the interim analyses, to be included the subject must have been randomized at least 90 days prior to the data freeze.

The treatment effect in this analysis is tested at the two-sided alpha level of 0.05.

Likwise, the As-Treated analysis will be repeated for the primary and secondary efficacy and safety outcomes.

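### Does the Fisher test at 0.01 in SAP 13.2 take the primary safety outcome, major hemorrhage, away from the 0.05 log-rank analysis?

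*SAP*

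**What the plan says.** SAP 13.2 has three parts. It first summarizes all SAEs by MedDRA term and treatment group. It then lists four specific outcomes (death from any cause, intracranial hemorrhage, major hemorrhage, minor hemorrhage), for which proportions with 95% confidence intervals are given by group. About those four it adds: "Expected rates of these events are based on historical data from the clopidogrel treated patients". A new paragraph then begins "Other serious adverse events will be reported by treatment group" and closes with the rule for the final comparison: "the cumulative incidences of these events are compared between the two treatment groups using Fisher's exact test at the two-sided alpha level of 0.01".

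SAP 3.2 names major hemorrhage as the primary safety outcome and says that safety is "evaluated by comparing rates of allcause death, intracranial hemorrhage, major hemorrhage, minor hemorrhage, and other treatment related complications and SAEs (see section 13.2".

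Elsewhere the SAP treats safety outcomes together with efficacy outcomes:

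- Section 6.2: "all efficacy and safety outcome measures are analyzed under the intent-to-treat (ITT) principle".
- Section 12.1.3, after setting out the log-rank test, the Cox hazard ratio and the 0.05 level: "the ITT analysis will be repeated for the primary and secondary efficacy and safety outcomes".
- Section 12.1.7, for the on-treatment analysis: "The treatment effect in this analysis is tested at the two-sided alpha level of 0.05", and then "the As-Treated analysis will be repeated for the primary and secondary efficacy and safety outcomes".
- Section 12.1.8 runs the aspirin-dose subgroup analysis on the primary safety outcome as well, with subgroup tests at 0.05.
- Section 12.5.1 lists the primary safety outcome by period (days 0 to 7 and 8 to 90; 0 to 30 and 31 to 90) with Cox hazard ratios and 95% confidence intervals, and sets 0.05 for each test.

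Protocol 10.1.3 lists major and intracranial hemorrhage among the secondary outcomes. Protocol 10.2.2 tests each secondary outcome at 0.05 and uses the primary-outcome strategy for most of them.

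**The concern.** The phrase *these events* in the last sentence of 13.2 can be read in two ways. Narrowly, it means the other SAEs of the sentence just before. Broadly, it also takes in the four listed outcomes. Two things invite the broad reading: the same phrase means those four one paragraph earlier, and SAP 3.2 refers the comparison of their rates to 13.2, where the Fisher test is the only between-group test.

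On the broad reading the primary safety outcome would have two tests and two significance levels: Fisher at 0.01 in 13.2, log-rank at 0.05 elsewhere. Whether an excess of major bleeding on clopidogrel is called significant could then turn on the grammar of one sentence. Estimation and safety stopping would not be affected. Hazard ratios with 95% confidence intervals are planned either way, and stopping for safety rests on DSMB judgment (Protocol 10.3.1, SAP 13.1).

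**Working it through.** **Which reading fits the text**

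1. *Antecedent.* In 13.2 the phrase appears twice, and each time it follows directly on what it would refer to: first the bulleted list, then the other SAEs. Consistent usage favors the narrow reading.
2. *Output already assigned.* The four listed outcomes have their own output in 13.2, proportions with 95% confidence intervals by group. That answers the pointer in 3.2, which speaks of comparing rates. The pointer may also attach only to the last item in its list, the SAEs.
3. *Fit with the rest of the SAP.* On the narrow reading, 13.2 gives a test level for other SAEs, and 12.5.2, which lists SAEs by class, states no level of its own. Nothing conflicts. An exact test at a strict level also suits a long list of sparse counts.
4. *Fit of the broad reading.* In Table A.3, major hemorrhage is codes 2, 4, 6 and 12. Codes 2, 4 and 6 make up hemorrhagic stroke, and code 12 is major hemorrhage other than intracranial. Section 12.5.1 tests both of these at 0.05. The broad reading would test the parts at 0.05 and their sum at 0.01, and would test the same outcome by period at 0.05. An author is unlikely to have meant that.

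**What the broad reading would cost**

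13.2 states no power or event count for this test, so there is no planned figure to reproduce.

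Inputs: 5,840 / 2 = 2,920 per arm (SAP 5.3, 1:1 allocation); 2% major hemorrhage on clopidogrel (SAP 13.2). The placebo rate is not stated. 1% is assumed, with a range of 0.5% to 1.5%. Protocol 8.1 estimates a 1% excess, but for major systemic hemorrhage only. A second case takes 1.7% and 1.0% from Protocol 2.4; those means are not specific to 90 days.

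Method: exact enumeration over two independent binomial counts without censoring, with the pooled two-proportion z-test standing in for the log-rank test. Disagreement means z-test p < 0.05 but Fisher p ≥ 0.01.

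| Clopidogrel vs placebo | z at 0.05 | Fisher at 0.05 | Fisher at 0.01 | Rules disagree |
|---|---|---|---|---|
| 2% vs 0.5% | >0.99 | >0.99 | 0.997 | 0.3% |
| 2% vs 1% | 0.889 | 0.869 | 0.690 | 19.9% |
| 2% vs 1.25% | 0.625 | 0.587 | 0.344 | 28.1% |
| 2% vs 1.5% | 0.309 | 0.275 | 0.112 | 19.8% |
| 1.7% vs 1.0% | 0.643 | 0.604 | 0.358 | 28.5% |

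Schoenfeld's log-rank formula gives 0.905 in place of 0.889 for 2% vs 1%, so the proxy is adequate. In that row the gap is 0.889 − 0.690 = 0.199, of which 0.869 − 0.690 = 0.179 comes from the level and only 0.020 from the choice of test.

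Example, 50 vs 29 events:

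- Risk ratio = 50/29 = 1.724.
- SE of its log = √(1/50 − 1/2920 + 1/29 − 1/2920) = 0.232.
- 95% CI = exp(0.545 ± 1.96 × 0.232) = 1.09 to 2.72.
- z-test p = 0.017; Fisher p = 0.023.

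The 95% interval excludes 1, yet the 0.01 rule would call the result not significant. With 29 placebo events, clopidogrel counts from 46 to 53 fall in this zone. In the other direction, with 1.5% in both arms, the chance of a false bleeding signal against clopidogrel is about 2.5% at 0.05 and about 0.4% with Fisher at 0.01.

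**The case for a change.** The best argument for a change is that no single SAP sentence gives the test and the level for major hemorrhage over the full 90 days. Section 12.5.1 covers the outcome by period and by its parts. The overall comparison rests on one closing line of 12.1.3, under a heading about efficacy, and the 0.05 there is stated for the primary analysis. Against that stands a section titled Safety Analyses with one explicit test at 0.01. Protocol 10.2.2 does not fully close the gap on method: it applies the primary strategy to most, not all, secondary analyses, and Protocol 10.2 names the log-rank test but not Cox. A primary safety outcome deserves better than inference, and a few words before unblinding would cost little.

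What stands is that the wording is loose and the scope of the last sentence must be inferred. What does not stand is that an analyst could equally well go either way. The method and level for safety outcomes recur across 12.1.3, 12.1.7, 12.1.8 and 12.5.1, and the 0.05 in Protocol 10.2.2 applies to each secondary outcome without exception. The broad reading also leads to the inconsistency between the whole and its parts shown above.

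Nor would an edit be quite as simple as it looks. A sentence sending all four listed outcomes to 12.5.1 would bring in new mismatches. Death is counted within 90 ± 14 days in 13.2, while 12.1.3 stops at day 90. Intracranial hemorrhage is unqualified in 13.2, while the specific intracranial items in 12.5.1 are symptomatic. Minor hemorrhage in 12.5.1 expressly includes asymptomatic intracranial hemorrhage, which 13.2 does not say.

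**Conclusion.** The concern does not call for a change. The ambiguity exists but is thin: the nearest antecedent in 13.2 is the other SAEs, that reading conflicts with nothing, and the rest of the SAP together with the 0.05 level in Protocol 10.2.2 puts major hemorrhage under the ITT log-rank test at two-sided 0.05, with a Cox hazard ratio and 95% confidence interval. An analyst who follows the plan as it naturally reads will do this, and the result will be sound. On that reading the effect is zero.

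The power loss (0.89 to 0.69 at 2% vs 1%) and the 0.3% to 28% disagreement arise only if the 0.01 rule were stretched to major hemorrhage. They also rest on assumed placebo rates, no censoring and a z-test proxy for the log-rank test. Even then, only the label of significance would change. The hazard ratio and its interval would be reported, secondary tests are declared exploratory (SAP 9, Protocol 10.2.2), and safety decisions during the trial belong to the DSMB. If the SAP is reopened for another reason, naming the other SAEs in that sentence would be a harmless tidy-up.
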